3.4 Study Drugs	
3.4.1 Omacetaxine-----	15
4. Data Collection -----	16
5. Adverse Event Reporting and Safety Monitoring -----	16
5.1. Data Safety Monitoring Plan -----	17
6. Statistical Considerations -----	18
7. References -----	19
Appendix A: The World Health Organization Classification of Myeloid Neoplasms---	21
Appendix B: ECOG Performance Status-----	22
Appendix C: Eligibility Check List and Registration Documents -----	23
Appendix D: Evaluations During Induction-----	24
Appendix E: Evaluations During Consolidation-----	25
Appendix F: Evaluations During Maintenance-----	26
Appendix G: Comorbidity Scoring-----	27
Appendix H: Quality of Life Questionnaire -----	28
Appendix I: Response Criteria-----	31
Appendix J: Omacetaxine Investigator's Brochure (see embedded document)-----	32

Appendix K: Omacetaxine Package Insert and Injection Worksheet (see embedded document) -----	33
Appendix L: Instructions for Omacetaxine Injection (see embedded document) -----	34
Appendix M: SAE Reporting and AE Log-----	35

SYNOPSIS

Title:

- Pilot Study of Omacetaxine for Consolidation and Maintenance for Patients Age ≥ 55 with AML in First Remission.

Objectives:

Primary Objectives:

- To assess the safety and tolerability of delivering omacetaxine for consolidation in adult patients age 55 and older with acute myelogenous leukemia (AML) in first complete remission following induction chemotherapy.
- To assess the safety and tolerability of delivering omacetaxine for maintenance in adult patients age 55 and older with acute myelogenous leukemia (AML) in first complete remission following 3 consolidation courses with omacetaxine.

Secondary Objectives:

- To assess the duration of remission.
- To evaluate disease-free survival (DFS).
- To evaluate overall survival (OS).
- To assess for minimal residual disease (MRD) by WT-1 PCR during consolidation and maintenance therapy with omacetaxine.

Treatment Plan:

The induction time will be the screening period for the study. Those who achieve remission and are willing and able to proceed with OMA consolidation/maintenance will continue onto the investigational part of the study.

Screening: Patients will receive one to two induction courses according to investigator discretion, with a 3+7 regimen (cytarabine/Ara-C and anthracycline) followed by up to one course of dose-adjusted high dose cytarabine. Each induction course consists of:

- Ara-C 100mg /m²/dose by continuous infusion daily for 7 days.

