- An anthracycline; either daunorubicin , idarubicin or mitoxantrone at standard doses daily for 3 days, starting on day 1.

The second induction will consist of dose-adjusted high dose Ara-C alone (1-1.5grm/m² Q12 hrs on day 1, 3, and 5, per standard of care). The timing for initiation of the second induction depends upon results of marrow done 14-21 days after the first induction according to standard of care practice.

- Patients who do not achieve remission at the conclusion of 2 inductions will be considered screen failures and offered alternative therapies.

Consolidation:

- Omacetaxine 1.25 mg/m² sub-cutaneously twice daily for 5 consecutive days every 28 (\pm 8) days for a total of 3 cycles.

Maintenance:

- Subjects in continuous remission after 3 cycles of consolidation with omacetaxine will receive maintenance omacetaxine 1.25mg/m² twice daily for 3days, every 28 days, for up to 6 cycles.

Sample size and patient selection:

- **Screening:** 45 patients with newly diagnosed, untreated AML eligible for induction chemotherapy. Patients who received 1-2 cycles of hypomethylating therapy for cytoreduction are also eligible.
- **Consolidation/maintenance:** 15 patients in first complete remission after 2 inductions.

Assessment of response:

- Bone marrow biopsy and aspirate will be obtained at day 14-21 of the 1st cycle, and at day 28 or at count recovery, whichever occurs first.
- Prior to each consolidation cycle, responses will be evaluated with a complete blood count (CBC) and bone marrow aspiration/biopsy to document continued remission.
- Bone marrow aspirate to confirm continuous remission will be obtained every 3 months during maintenance, and as clinically indicated thereafter.

Statistical Methods:

- This study is an open label, pilot study. Continuous data will be described using descriptive statistics (n, mean, median, minimum, and maximum) while discrete data will be described using frequency counts and percentages.

Time line: 2-3 years, based on previous accrual in the target population.

1. BACKGROUND:

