High dose cytarabine (HiDAC, doses $> 1.5 \text{ g/m}^2/\text{d}$) administered during induction results in improved recurrence-free and overall survival in younger AML patients < 60 ,¹² but is associated with increased toxicities in older patients^{13,14}. We have recently reported on the safety and efficacy of modified HiDAC induction for newly diagnosed patients ≥ 60 with AML ([name] et al. ASCO 2010). HiDAC induction was well-tolerated, associated with high CR rates (69%), and comparable early mortality to standard dose cytarabine induction (19%). In our series, 37/59 (63%) patients were able to receive the 2 planned inductions. Of the 41/59 (69%) that achieved remission, 6, 11, and 10 patients received 1, 2, and 3 consolidations with HiDAC, respectively. **However, despite high initial CR rate (69%) and the delivery of standard consolidation in 80%, the median relapse-free survival was 11 months, and most patients died from relapsed leukemia.** Therefore, exploring alternative consolidation regimens is desirable. Since the current study opened, we have learned that prospectively, our patients did not tolerate the 2 consecutive cycles of modified HiDAC/daunorubicin due to cardiac toxicity, and have amended the protocol to limit induction to only 1 cycle of standard infusional cytarabine $100\text{mg}/\text{m}^2$ over 24hrs. daily $\times 7$ days and an anthracycline (daunorubicin, idarubicin, or mitoxantrone at standard doses). At count recovery or sooner if residual leukemia is present at the end of induction, 1 cycle of dose-adjusted high dose cytarabine can be administered (1-1.5gm/m² IV Q12hrs. on days 1,3, and 5, per standard of care).

1.3 Consolidation Therapy for Older Patients with AML.

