2. STUDY OBJECTIVES

Primary Objectives:

- To assess the safety and tolerability of delivering omacetaxine for consolidation in adult patients age 55 and older with acute myelogenous leukemia (AML) in first complete remission following induction chemotherapy.
- To assess the safety and tolerability of delivering omacetaxine for maintenance in adult patients age 55 and older with acute myelogenous leukemia (AML) in first complete remission following 3 consolidation courses with omacetaxine.

Secondary Objectives:

- To assess the duration of remission.
- To evaluate disease-free survival (DFS).
- To evaluate overall survival (OS).
- To assess for minimal residual disease (MRD) during consolidation and maintenance therapy with omacetaxine.

3. RESEARCH DESIGN AND METHODS:

3.1 Patient Selection:

3.1.1 Inclusion Criteria:

1. Diagnosis of AML including de novo, secondary, or with an antecedent hematologic disorder [AHD] according to the World Health Organization (WHO) criteria²⁵ (**Appendix A**).
2. Age \geq 55 years.
3. Patient eligible for standard induction chemotherapy based on ECOG PS and vital organ function at the discretion of the treating physician.
4. Patients who received 1-2 cycles of hypomethylating therapy (decitabine azacitidine) are eligible.
5. Provide signed written informed consent.
6. Be able to comply with study procedures and follow-up examinations.
7. Be non-fertile or not pregnant or lactating & agree to use birth control during the study through the end of last treatment visit.
8. Adequate renal and hepatic function **at the time of second registration**:
 - a. Total bilirubin \leq 1.5 x institutional Upper Limit of Normal (ULN); and
 - b. Aspartate aminotransferase (AST) and alanine aminotransferase (ALT) \leq 2.5 x ULN; and
 - c. Serum creatinine \leq 1.2 times the upper limit of normal.
9. ECOG performance \leq 2 (**Appendix B**) **at the time of second registration**:
10. Patients with a history of carcinoma in remission, on no therapy or on hormonal therapy for the adjuvant treatment of breast carcinoma or prostate carcinoma are included in the study.

3.1.2 Exclusion Criteria:

1. Diagnosis of acute promyelocytic leukemia (APL, French-American-British [FAB] classification M3 or WHO classification of APL with t (15;17)(q22;q12), (*PML/RARA* and variants).
2. Prior treatment with omacetaxine
3. Relapsed or refractory AML.

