 - **Complete Remission (CR):** Normocellular marrow with < 5% blasts, absence of auer rods and of any unique phenotype identical to what was found in the pretreatment specimen, with ANC $\geq 1 \times 10^9/L$ and platelet count $\geq 100 \times 10^9/L$, and transfusion independence, as well as no residual evidence of extramedullary AML.
 - **Complete Response with incomplete blood count recovery (CRi):** Meets criteria for CR above, except for residual neutropenia (ANC < $1 \times 10^9/L$) or thrombocytopenia (platelets < $100 \times 10^9/L$)
 - **Complete Response with incomplete platelet recovery (CRp):** Meets criteria for CR above, but platelets are < $100 \times 10^9/L$.
 - **Cytogenetic Complete Remission (CRc):** Disappearance of cytogenetic abnormalities thought to be associated with the AML.
 - **Molecular Complete Remission (CRm):** Disappearance of molecular abnormalities thought to be related to the AML.
 - **Treatment failure:**
 - **Resistant disease:** Patient survives ≥ 7 days post-chemotherapy and has persistent AML in blood or bone marrow.
 - **Aplasia:** Patient survives ≥ 7 days post-chemotherapy, but dies while cytopenic, with an aplastic bone marrow.
 - **Morphologic relapse:** Reappearance of blasts post-chemotherapy in peripheral blood or bone marrow.
 - **Molecular/cytogenetic relapse:** Reappearance of molecular or cytogenetic abnormality.
 - **Clearance of Leukemia at the day 14 marrow:** < 5% blasts in a hypocellular marrow (<15% cellularity).

- **Overall survival (OS):** Time from entry onto trial until death from any cause.
- **Relapse free survival (RFS):** Time from Remission (CR, CRi, CRp) until disease relapse or death from any cause.
- **Event free survival (EFS):** Time from entry onto trial to treatment failure/relapsed disease, or death from any cause.
- **Remission duration:** Time from date of CR (or CRp, CRi) until disease relapse.

3.3.3 Safety Assessment and Study Tests:

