Number of DLTs to Stop Trial	> 1	> 1	> 3	> 3	> 4	> 4	> 4	> 5	> 5	> 6	> 6	> 6	> 7
Probability of falsely terminating the trial		0.08	0.03	0.07	0.03	0.06	0.10	0.05	0.08	0.04	0.07	0.10	0.05

Feasibility: Feasibility is defined as delivery of 9 cycles of therapy for at least 2/3 of the patients. The proportion of patients with full treatment delivery will be estimated with an exact 95% confidence interval.

Futility: Based on our previous data showing a median relapse-free survival of 13.8 months, we will consider our consolidation/maintenance regimen futile if $\geq 80\%$ of those entering in CR relapse during consolidation/maintenance.

Kaplan-Meier curves will be used to estimate the distribution of time to relapse, relapse free survival, and overall survival.

Analysis of survival outcomes (OS, EFS, RFS) for patients who undergo transplantation in CR will include censoring and no censoring at the time of transplantation.

References:

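### RFS and remission duration are timed from remission, but patients join the omacetaxine cohort later, so ordinary Kaplan-Meier curves for that cohort would count guaranteed event-free time

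*Combined protocol and SAP*

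**What the plan says.** **Time origin.** Section 3.3.2, repeated in Appendix I, defines RFS as "Time from Remission (CR, CRi, CRp) until disease relapse or death from any cause" and remission duration as "Time from date of CR (or CRp, CRi) until disease relapse".

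**Entry to the omacetaxine cohort.** The Synopsis treats induction as screening: "Those who achieve remission and are willing and able to proceed with OMA consolidation/maintenance will continue onto the investigational part of the study". It plans for "45 patients with newly diagnosed, untreated AML eligible for induction chemotherapy" at screening and, for omacetaxine, "15 patients in first complete remission after 2 inductions". Section 3.1.1 applies the organ-function and ECOG limits "at the time of second registration". Section 3.1.2 excludes relapsed disease. The Synopsis also requires a blood count and marrow before every consolidation cycle to confirm that remission continues.

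**Between remission and entry.** Under section 1.2, at count recovery after the first induction, or sooner if leukaemia remains, "1 cycle of dose-adjusted high dose cytarabine can be administered". No maximum interval from remission to second registration is set.

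**Analysis.** Section 6 states: "Kaplan-Meier curves will be used to estimate the distribution of time to relapse, relapse free survival, and overall survival". It gives no delayed entry, landmark or alternative origin. Its only special handling is to analyse survival outcomes with and without censoring at transplantation. It does not say whether the curves cover the omacetaxine patients or everyone who remits among those screened.

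**The concern.** This is left truncation, also called immortal time. The clock starts at remission, but a patient becomes visible to the omacetaxine analysis only at second registration. A patient who remits and then relapses or dies before that point is never in the cohort. An ordinary Kaplan-Meier curve still treats every cohort member as having been at risk since remission, so its first stretch is flat by construction.

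Remission duration is the first secondary objective, and RFS is one of the quantities section 6 will plot. The study is presented in section 1.6 as the step before an efficacy phase II trial, so its RFS is likely to be read beside the institution's own earlier figures: a median of 11 months in section 1.2 and 13.8 months in section 6. Event-free time that no cohort member could have lost would then be credited to omacetaxine. The amount would also differ between patients, depending on whether a second course followed remission.

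**Working it through.** The plan gives no event count, power or precision for RFS or remission duration, so there is no figure of its own to reproduce. The check has two parts: whether a gap can exist, and what it would do.

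**1. Can there be a gap?**
- Near zero: section 3.3.2 calls for a marrow at count recovery after induction. CR requires ANC of at least 1 and platelets of at least 100 (×10⁹/L), the same thresholds that section 3.3.1 sets for omacetaxine cycles. A patient whose CR is first documented just before second registration contributes almost no guaranteed time.
- Longer: under section 1.2 a patient already in remission after the first course may have a cytarabine course before omacetaxine. RFS may also start at CRi or CRp, when counts are still low, while the start of omacetaxine is tied to count recovery (or, with prior MDS, recovery to the pre-AML baseline).

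So the gap varies between patients and its length is unknown.

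**2. Size of the bias**

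Inputs: true median RFS m = 11 months (section 1.2) or 13.8 months (section 6). Assumptions: constant hazard, no drug effect, and a fixed gap of g months between remission and registration.

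S(t) = 0.5^(t/m). Among patients event-free at g, an ordinary curve from remission estimates S(t)/S(g) = 0.5^((t−g)/m). Its median is m + g. The share of remitters lost before entry is 1 − 0.5^(g/m).

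| m | g | Apparent median | Apparent 12-month RFS | Lost before entry |
|---|---|---|---|---|
| 11 | 0 | 11 | 0.469 (true) | 0 |
| 11 | 0.5 | 11.5 | 0.484 | 3.1% |
| 11 | 1 | 12 | 0.500 | 6.1% |
| 11 | 2 | 13 | 0.533 | 11.8% |
| 13.8 | 0 | 13.8 | 0.547 (true) | 0 |
| 13.8 | 0.5 | 14.3 | 0.561 | 2.5% |
| 13.8 | 1 | 14.8 | 0.576 | 4.9% |
| 13.8 | 2 | 15.8 | 0.605 | 9.6% |

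Example: m = 11, g = 2 gives 0.5^(10/11) = 0.533, against 0.5^(12/11) = 0.469. For gaps of 0.5 to 2 months the 12-month estimate is too high by about 0.01 to 0.06.

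**3. Against sampling error**

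With 15 patients and no censoring, the SD of a 12-month proportion near 0.469 is √(0.469 × 0.531 / 15) = 0.129. Simulated cohorts of 15 gave 0.12 to 0.13.

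**4. Does delayed entry remove it?**

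Large-sample simulation with variable gaps, median RFS in months:

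| Gap (assumed) | True | Ordinary | Delayed entry |
|---|---|---|---|
| Uniform 0–2 | 11 | 11.9 | 10.9 |
| Uniform 0–2 | 13.8 | 14.7 | 13.7 |
| Uniform 0.5–3 | 11 | 12.7 | 11.6 |
| Uniform 0.5–3 | 13.8 | 15.5 | 14.2 |

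When some patients enter at remission, delayed entry recovers the truth. When nobody enters before 0.5 months, it estimates RFS conditional on reaching 0.5 months (expected medians 11.5 and 14.3), so a small excess remains.

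**The case against.** **The analysis set is not stated.** Patients consent before induction, and the section 3.3.2 list also holds induction outcomes such as resistant disease and day-14 clearance. RFS in everyone who remits among the 45 is a possible reading and carries no truncation. This stands as a condition on the point. However, such a curve would mix in patients who never received omacetaxine, while the objectives concern omacetaxine. The cohort of 15 is the more natural set.

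**The gap may be negligible.** This also stands. The second course is optional, and nothing shows that a full course after documented remission is typical. A reader might infer a definite or large overstatement; the documents support only the direction and a range that includes zero.

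**The effect is below the noise, and no decision uses it.** This is correct. The trial is a descriptive pilot with safety and tolerability as primary objectives. A reader might infer that the futility rule is distorted, because section 6 introduces it with the 13.8-month historical median. It is not: the rule is the proportion, among those entering in CR, who relapse while on consolidation or maintenance, and it uses no clock from remission. What remains is that a one-directional bias does not average out and that a confidence interval does not reveal it.

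**DFS.** A reader might carry the point over to disease-free survival, a named secondary objective. Section 3.3.2 and Appendix I define RFS and EFS but not DFS, so this follows only if DFS is meant as RFS.

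**The remedy has limits.** With at most 15 patients, delayed entry leaves small early risk sets, and one early event could move the whole curve. Neither delayed entry nor a later origin undoes selection on ECOG, organ function or willingness to continue. Both limits are real; the first favours reporting from second registration.

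**Conclusion.** The point holds conditionally. If section 6's ordinary Kaplan-Meier curves are drawn from remission for the patients who pass second registration, RFS and remission duration are biased upward by the guaranteed event-free gap. With a constant hazard and an assumed gap of 0 to 2 months, a true median of 11 months would appear as 11 to 13, and one of 13.8 as 13.8 to 15.8. Twelve-month RFS would move from 0.469 to at most 0.533, or from 0.547 to at most 0.605.

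The bias is smaller than sampling error at this sample size and changes no stopping, safety or futility decision. It matters for how the secondary results are read, especially beside the historical medians. It is worth correcting because the correction is nearly free.

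**What to change.** In section 6:

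1. State that the analysis set for RFS and remission duration is the patients who pass second registration.
2. Report both endpoints from second registration.
3. If the remission origin is also kept, let each patient enter the risk set at second registration. Say that early risk sets are small and that the estimate is conditional on the earliest entry time.
4. Record the remission date and list each patient's remission-to-registration interval. The eligibility checklist and adverse event log in the appendices have no field for remission date, and the case report forms are not in the documents, so confirm that it is captured.
5. Do not set the result beside the historical median RFS unless that is measured from a matching point. The documents do not give the time origin of either historical median. In the series in section 1.2, 41 patients remitted and 6 + 11 + 10 = 27 are listed as having received consolidation (66%; the text says 80%). On either figure, some remitters never reached consolidation.

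Cost: a few sentences, a standard software option and one listing, with no change to treatment or visits. Reported medians would be slightly shorter, and a delayed-entry curve would be unstable at its start.

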Cycle #1: Cytarabine at $100\text{mgm}^2/\text{dose}$ via continuous infusion daily for 7 days, starting on day 1.

Daunorubicin, idarubicin, or mitoxantrone at standard dosing daily for 3 days, starting on day 1.

Cycle #2: Cytarabine 1- $1.5\text{gm}/\text{m}^2/\text{dose}$ IV twice daily on days 1, 3 and 5.

- Study specific evaluations during induction (See **Appendix D**)

B. Consolidation:

- Omacetaxine 1.25 mg/m² sub-cutaneously twice daily for 5 consecutive days every 28 (\pm 8) days for 3 cycles, provided that prior to the next planned treatment cycle, the patient's absolute neutrophil count (ANC) recovers to $\geq 1 \times 10^9/L$ and the platelet count recovers to $\geq 100 \times 10^9/L$. Patients with history of or suspected MDS prior to AML who fail to recover their ANC and platelets after induction chemotherapy, may start omacetaxine upon recovery to baseline pre-AML ANC and platelet count. Omacetaxine can be administered at Emory/Winship Cancer Institute or by self- injection at home.
- Evaluations during consolidation (see **Appendix E**)

C. Maintenance:

- Patients in continuous remission after 3 cycles of consolidation will receive maintenance omacetaxine 1.25mg/m² twice daily for 3 days, every 28 days for up to 6 cycles, provided that prior to the next planned treatment cycle, the patient's absolute neutrophil count (ANC) recovers to $\geq 1 \times 10^9/L$ and the platelet count recovers to $\geq 100 \times 10^9/L$. Patients with history of MDS prior to AML who fail to recover their ANC and platelets after induction chemotherapy, may start omacetaxine upon recovery to baseline pre-AML ANC and platelet count. Omacetaxine can be administered at Emory/Winship Cancer Institute or by self- injection at home.
- Evaluations during maintenance (see **Appendix F**)

D. Supportive Care (these guidelines are not protocol requirements as these as standard of care practices):

- Standard anti-microbial prophylaxis will be instituted for every patient enrolled in this study. Suggestions include: anti-viral (acyclovir or valacyclovir), anti-bacterial (fluoroquinolone, doxycycline, or standard alternative) and anti-fungal (azole or micafungin) prophylaxis will be initiated at the onset of neutropenia according to our institutional standard. Patients experiencing fever will be treated according to institutional practice, with blood cultures, imaging of suspected areas of infection, and empiric antibiotics targeted at the suspected cause of fever.

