Toxicities will be monitored by history, physical examination, and laboratory monitoring (CBC, serum chemistries to include renal and liver function tests) weekly during consolidation and monthly during maintenance according to standard of care (Appendices D-F). Toxicity will be assessed according to the NCI Common Toxicity Criteria Version 4.0 (available at the NCI web site <http://ctep.cancer.gov/reporting/ctc.html>). Adverse events will be monitored on an ongoing basis. No AEs will be collected during the screening period (the time from diagnosis to completion of the standard of care inductions).

3.3.4 Dose Modifications and Stopping Rules:

A. Omacetaxine

- ***Hematological toxicity:***

- The following table summarizes dose adjustments for hematological toxicity during consolidation and maintenance with Omacetaxine and are based on time to count recovery to < grade 2 hematological toxicity. Hematologic toxicity only refers to WBC/neutrophils and platelets and not hemoglobin/hematocrit, given that anemia is expected and may not resolve after chemotherapy regardless of AML-status. Dose-reductions and delays do not apply to anemia.

Time to resolution to < grade 2 hematologic toxicity (days)	Action 1	Action 2: Hematologic toxicity after 1 st dose reduction
≤ 36	No dose reduction	No dose reduction
> 36 and < 50	20% dose reduction, i.e. omacetaxine 1.25 mg/m ² sub-cutaneously twice daily for 4 days during consolidation, or 1.25mg/m ² twice daily for 3 days during maintenance	Additional 25% dose reduction, i.e. omacetaxine 1.25 mg/m ² sub-cutaneously twice daily for 3 days during consolidation, or 1.25mg/m ² twice daily for 2 days during maintenance
> 50	Perform bone marrow aspirate and biopsy. If relapse – patient will be taken off study. If hypoplastic marrow (cellularity < 10%), reassess after 2 weeks. If recovery achieved within 2 weeks post-marrow assessment, resume omacetaxine after 60% dose reduction; i.e. omacetaxine 1.25 mg/m ² sub-cutaneously twice daily for 3 days during consolidation, or 1.25mg/m ² twice daily for 2 days during maintenance If no recovery 2 weeks post-marrow assessment, patient will be taken off study.	No further dose reduction. Patient will be taken off study

- ***Non-hematological toxicity:***

- Patient with grade III-IV non-hematological toxicity (deemed at least “possibly” related to omacetaxine) will have study drug held until toxicity has recovered to grade 1 or less. Treatment may resume after 20% dose reduction.

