- Patient who develop grade II non-hematological toxicity that is related to omacetaxine will have study drug held at treating physician’s discretion, until toxicity has recovered to grade 1 or less. Treatment will resume after 20% dose reduction.
- If grade III-IV non-hematological toxicity recurs after dose-reduction, the patient will discontinue protocol therapy.
- If grade III-IV non-hematological toxicity does not resolve to grade 1 or less by day 36 of therapy with omacetaxine, then patient will be taken off study.

B. Cytarabine

The following guidelines are not protocol requirements given that patients are receiving Institutional standard induction.

Doses of cytarabine can be **reduced** during the second induction in cases of decrease in the calculated creatinine clearance $> 20\%$ but less than 50% . HiDAC will be discontinued and patient taken off study if neurotoxicity occurs at any time during HiDAC therapy.

C. Daunorubicin, Idarubicin, or mitoxantrone

The following guidelines are not protocol requirements given that patients are receiving Institutional standard induction.

- Drug will be withheld and patients will be withdrawn from the study, if they experience a clinically significant decrease in left ventricular ejection fraction, leading to a diagnosis of symptomatic congestive heart failure.
 - Adjustments for hepatic and renal dysfunction will conform to recommendation from the package inserts and standard practice.

D. Stopping Rules

- Omacetaxine will be **discontinued** in cases of
 - Delay in recovery of ANC to $\geq 1,000/\text{mcL}$ and platelets to $\geq 100,000/\text{mcL}$ or to baseline ANC and platelets (for patients with history of underlying MDS) after 50 days.
 - Grade III-IV irreversible non-hematological toxicity attributable to omacetaxine
 - Recurrence of grades III-IV non-hematological toxicities after dose-reduction.
 - Recurrent leukemia.
 - Patient’s or treating physician’s request.

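### Section 3.3.4: the maintenance 20% dose reduction is printed as the full dose, and one case of recovery delayed beyond 50 days is told both to resume and to stop

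*Combined protocol and SAP*

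**What the plan says.** **Full maintenance dose.** The Synopsis gives omacetaxine 1.25 mg/m² "twice daily for 3days, every 28 days, for up to 6 cycles". Section 3.3.1 C agrees: "twice daily for 3 days, every 28 days for up to 6 cycles".

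**Delay of more than 36 and fewer than 50 days.** In the table of section 3.3.4 A, the Action 1 cell orders a "20% dose reduction, i.e. omacetaxine" and spells it out as 1.25 mg/m² twice daily for 4 days in consolidation, or "twice daily for 3 days during maintenance". The second column is headed "Action 2: Hematologic toxicity after" a first dose reduction. It takes a further 25% off, printed as 3 days in consolidation and 2 days in maintenance.

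**Delay of more than 50 days.** Action 1 calls for a marrow. Relapse takes the patient off study. A hypoplastic marrow is reassessed after two weeks: "If recovery achieved within 2 weeks post-marrow assessment, resume omacetaxine after 60% dose reduction", printed as 3 days in consolidation and 2 days in maintenance. Without recovery in that time the patient goes off study. Under Action 2 the entry is "No further dose reduction. Patient will be taken off study".

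**Section 3.3.4 D, Stopping Rules.** Omacetaxine is discontinued when ANC and platelets are delayed in reaching 1,000/mcL and 100,000/mcL, "or to baseline ANC and platelets (for patients with history of underlying MDS) after 50 days". No exception is written for later recovery, and there is no reference back to the table.

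**Section 6** takes its definition of DLT from section 3.3.4.

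**The concern.** The reduced maintenance dose is the same as the unreduced one. A patient whose counts recover late during maintenance would get the full dose again at the step meant to lower it. The count-recovery condition before each cycle (section 3.3.1 C) and the blood count schedule (Appendix F) still apply, but they delay or monitor treatment and do not reduce the dose. This cell is also the only place where a 20% maintenance cut is turned into days; the non-haematological rules call for 20% and print no schedule.

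The slip carries into the next column, which presumes a reduction has already been made. If this patient's next delay exceeds 50 days, Action 2 takes the patient off study, while Action 1 allows treatment to resume at 2 days after recovery. The text does not say which applies.

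The second problem is a direct conflict: the table and section D give opposite instructions for the same patient. Safety and tolerability of omacetaxine in consolidation and in maintenance are the two primary objectives, and section 6 relies on section 3.3.4 to say what a DLT is.

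**Working it through.** **1. Dose per cycle**

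Inputs: 1.25 mg/m² per injection, two injections a day, days as printed in sections 3.3.1 and 3.3.4 A. Daily dose = 1.25 × 2 = 2.5 mg/m². Dose per cycle = 2.5 × days. Cut = 1 − reduced ÷ full.

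| Step | Label | Consolidation | Maintenance |
|---|---|---|---|
| Full dose | – | 5 days, 12.5 mg/m² | 3 days, 7.5 mg/m² |
| >36 and <50 days, Action 1 | 20% | 4 days, 10.0 mg/m², cut 20% | 3 days, 7.5 mg/m², **cut 0%** |
| >36 and <50 days, Action 2 | further 25% | 3 days, 7.5 mg/m², 25% below Action 1 | 2 days, 5.0 mg/m², 33.3% below Action 1 |
| >50 days, Action 1, recovered | 60% | 3 days, 7.5 mg/m², cut 40% | 2 days, 5.0 mg/m², cut 33.3% |

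The 20% and 25% labels reproduce exactly in consolidation. The 20% label does not reproduce in maintenance. A true 20% cut there is 0.8 × 7.5 = 6.0 mg/m², which is 1.0 mg/m² twice daily for 3 days. In whole injection days at 1.25 mg/m² it would need 0.8 × 3 = 2.4 days.

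The maintenance Action 2 cell is not counted as an error. The cumulative target is 0.8 × 0.75 = 0.60 of full dose, and 0.60 × 3 = 1.8 days, so 2 days is ordinary rounding.

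The 60% label fits neither phase as a cut: a true 60% cut would leave 2 days in consolidation and 1.2 in maintenance. In consolidation 60% is the share kept (7.5 ÷ 12.5); in maintenance the share kept is 67% (5.0 ÷ 7.5). The days are explicit, so this is a label error only.

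**2. Excess over a true 20% cut**

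Excess = (7.5 − 6.0) × remaining cycles, out of 6 maintenance cycles, assuming the patient stays at this step to the end.

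| First delay follows maintenance cycle | Remaining cycles | Excess (mg/m²) |
|---|---|---|
| 1 | 5 | 7.5 |
| 2 | 4 | 6.0 |
| 3 | 3 | 4.5 |
| 4 | 2 | 3.0 |
| 5 | 1 | 1.5 |

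The largest value equals one full maintenance cycle.

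**3. Delay beyond 50 days: table against section D**

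| Situation after day 50 | Table, 3.3.4 A | Section D |
|---|---|---|
| Relapse on marrow | off study | discontinue |
| Hypoplastic, no recovery in 2 weeks | off study | discontinue |
| Delay after a prior reduction | off study | discontinue |
| First delay, hypoplastic, recovers within 2 weeks | **resume at reduced dose** | **discontinue** |

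Only the last row conflicts. The two texts also measure recovery differently: the table uses resolution to below grade 2, section D uses stated counts or the MDS baseline. The conflict is therefore confined to a patient who meets neither standard at day 50.

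**4. Margin in the section 6 criterion**

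With n = 15, the exact one-sided 95% upper limit U for x DLTs solves P(X ≤ x | 15, U) = 0.05, that is, the 0.95 quantile of Beta(x + 1, 15 − x).

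- x = 1: U = 27.9%, within the 30% ceiling.
- x = 2: U = 36.3%, above it.

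The verdict turns between one DLT and two, so the classification of a single patient can decide it.

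**The case against.** The strongest reply is that the printed dose may be intended. If every fraction is rounded up to whole days and 60% is read as the share kept, all the cells fit: 4, 3 and 3 days in consolidation, and 2.4 to 3, 1.8 to 2 and 1.8 to 2 in maintenance. This cannot be excluded. But the documents state no rounding rule, 2.4 days is nearer to 2, and the cell calls a zero cut a 20% reduction. Even if 3 days is intended, the label is wrong and the reader still needs to know whether the step counts as a first reduction.

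Several narrower points stand:

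- A patient already reduced in consolidation has had a first reduction, so Action 2 can properly apply to that patient in maintenance. The problem concerns patients whose first qualifying delay occurs during maintenance.
- The exposure is modest. 7.5 mg/m² per cycle is also the lowest reduced consolidation level, count recovery is required before each cycle, and the treating physician may stop treatment at any time.
- The resume-or-discontinue conflict needs an uncommon sequence of events. A reader could let the detailed table override the general list, but the protocol does not say so, and the list is headed as stopping rules.
- Section 3.3.4 does not label any event a DLT. That is a separate gap: settling whether the patient resumes would not by itself settle DLT status. The upper limits above describe how narrow section 6 is, not the effect of this defect.

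**Conclusion.** Both points hold; the text is wrong as written. The maintenance step labelled 20% is a 0% cut (7.5 against 6.0 mg/m² per cycle), with an excess of 1.5 to 7.5 mg/m² over the remaining cycles if the patient stays at that step. For a first delay beyond 50 days with a hypoplastic marrow, neither recovery standard met at day 50, and recovery within two weeks of the marrow assessment, the table and section D give opposite instructions. The 60% label is a minor error that changes no dose.

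The dose result rests only on the printed schedules. The documents give no rates for either event, so neither the number of patients affected nor any effect on the trial's conclusion can be stated. Correction is still required because the error sits in a toxicity dosing instruction and a stopping rule, and can be removed by wording alone.

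**What to change.** 1. **Maintenance Action 1 cell.** Print a real reduction: 1.0 mg/m² twice daily for 3 days (6.0 mg/m², exactly 20%), or 1.25 mg/m² twice daily for 2 days (5.0 mg/m², a 33% cut, relabelled to match). If 2 days is chosen, the maintenance Action 2 cell must also change, because it is already 2 days. Alternatively, state that no reduction applies in maintenance at this step and which column governs the next delay.
2. **Section D and the row for delays beyond 50 days.** Either add to section D an exception for a first occurrence with hypoplastic marrow that recovers within two weeks of the marrow assessment, or delete the resume option from the table. In the same edit, state whether that patient counts as a DLT for section 6, and use one recovery threshold in both places.
3. **The 60% label.** Replace it with the cuts the printed days give: 40% in consolidation and 33% in maintenance.

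Which dose and which rule are intended is for the sponsor to decide. The cost is amendment wording only; sample size and visits are unchanged.
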